6.4.2 Pharmacodynamics

Percentage of platelet aggregation inhibition will be summarized using descriptive statistics over time by dose and ethnic group. Mean (or median) percentage of platelet aggregation versus time by dose and ethnic group will be presented graphically. Differences (Japanese – Caucasian) in mean (or median) percentage of platelet aggregation inhibition will be summarized by dose.

6.4.3 Safety

All subjects who receive at least one dose of study medication will be included in the analysis of safety.

6.4.3.1 Adverse events

All adverse events will be listed for each subject including the assigned system organ class (SOC) and preferred term using the Medical Dictionary for Regulatory Activities (MedDRA). All adverse events occurring following the first dose of study drug will be summarized by SOC, preferred term, dose and ethnic group.

6.4.3.2 Bleeding times

Bleeding time and change from baseline in bleeding time will be summarized by time after dose, dose and ethnic group using descriptive statistics. Baseline will be defined as the pre-dose measurement taken at each visit. Differences in change from baseline (Japanese – Caucasians) will also be summarized by time and dose. Mean bleeding time versus time by dose and ethnic group will be displayed graphically. Individual bleeding times versus time will also be displayed graphically by dose and ethnic group.

6.4.3.3 Laboratory and vital sign data

Hematology, clinical chemistry, urinalysis and vital sign data will be listed and summarized by dose, ethnic group and measurement time. Values that are out of the lab reference range will be flagged in the listings. Qualitative urinalysis data will be summarized using the number of subjects with results of negative, trace or positive.

6.4.3.4 ECG

All ECG intervals data will be summarized using descriptive statistics by dose, visit and measurement time. Change from baseline in QTc will be summarized using descriptive statistics by dose and assessment time. There will be a set of baseline measures taken at each visit. Baseline will be the ECG measures taken on the pre-dose day at the same time relative to the expected dosing time for the current visit.

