1.2 Rationale

AZD6140 has not been administered to Japanese subjects and the differences in safety/pharmacokinetics/pharmacodynamics between Japanese and Caucasian subjects have not been investigated. The purpose of this study is to investigate the safety of AZD6140 in Japanese subjects and to explore the pharmacokinetic (PK) profile of AZD6140 in groups of healthy subjects of both Japanese and Caucasian ethnicity. Additionally, the level of platelet aggregation inhibition will be evaluated by bleeding time assessment and optical aggregometry. It is anticipated that data from this study will be used to help further clinical development of AZD6140 in Japan, and the use of first, second and/or third generation Japanese data will be included. After single dose administration of AZD6140, the PK parameters of AZD6140 were linear across the dose range of 30 mg to 400 mg in the 2 single ascending dose studies (SC-532-5169 and SC-532-5171) where a good correlation between the plasma concentration of AZD6140 and the degree of inhibition of platelet aggregation was observed. The assessment of both PK and PD endpoints will aid in the analysis should significant differences be observed between the two groups. The cumulative data from the studies in human subjects to date demonstrate a good safety profile for doses up to and including 600 mg. Therefore, if significant differences in pharmacokinetics or pharmacodynamics should be observed between the two groups, we would anticipate an acceptable margin for subject safety.

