2. STUDY OBJECTIVES

2.1 Primary objectives

The primary objective of this study is:

- To assess the safety and tolerability of single ascending oral doses of AZD6140 administered to healthy Japanese and Caucasian subjects by means of incidence and severity of adverse events, 12-lead ECG, vital signs, laboratory parameters and physical examinations.

The secondary objectives of this study are:

- To assess and compare the pharmacokinetics in healthy Japanese and Caucasian subjects following single ascending oral doses of AZD6140 by assessment of C_{max} and AUC.
- To assess and compare the pharmacodynamics in healthy Japanese and Caucasian subjects following single ascending oral doses of AZD6140 by assessment of platelet aggregation inhibition and bleeding time.

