The highest dose of 600 mg was chosen based on safety and tolerability of multiple oral doses of 600 mg in Caucasians. The results in the repeated dosing study with healthy male Caucasian subjects (50 mg od, 200 mg od, 50 mg bid) showed that C_{max} of AZD6140 at steady state were approximately 1.0, 1.3 and 1.5 times higher than those after the single administration of the same dose and C_{max} of AR-C124910XX 1.2, 1.4 and 1.5 times higher, respectively. The future daily dose is now assumed to be around 400 mg. However, to fully explore the tolerability, safety, pharmacokinetics and pharmacodynamics of the Japanese subjects 600 mg was chosen as the upper exposure limit to ensure comparable safety and tolerability between Japanese and Caucasian subjects.

A genetic analysis will also be carried out to explore genetic factors important in the disposition of AZD6140 and response to AZD6140. Since this study is not designed or powered for genetic analysis, the resultant genetic data are considered exploratory and will not form part of the clinical study database or the clinical study report. The results of this study may be pooled with genetic results from other studies on AZD6140 to generate hypotheses to be tested in future studies.

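### Section 6.4.3.4 leaves ethnic group out of the ECG interval and QTc summaries, so the specified tables pool Japanese and Caucasian subjects at each dose

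*Protocol*

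**What the plan says.** Section 6.4.3.4 of the protocol sets out two ECG summaries. For intervals: "All ECG intervals data will be summarized using descriptive statistics by dose, visit and measurement time". For QTc: "Change from baseline in QTc will be summarized using descriptive statistics by dose and assessment time". Ethnic group appears in neither.

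The primary objective in Section 2.1 is "To assess the safety and tolerability of single ascending oral doses of AZD6140 administered to healthy Japanese and Caucasian subjects", and the means are listed as "by means of incidence and severity of adverse events, 12-lead ECG, vital signs, laboratory parameters and physical examinations". Section 1.2 gives the purpose: "The purpose of this study is to investigate the safety of AZD6140 in Japanese subjects". Section 3.2 says the 600 mg upper limit was chosen "to ensure comparable safety and tolerability between Japanese and Caucasian subjects".

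The neighbouring safety sections do use ethnic group. Section 6.4.3.3 reads: "Hematology, clinical chemistry, urinalysis and vital sign data will be listed and summarized by dose, ethnic group and measurement time". Section 6.4.3.1 (adverse events) and Section 6.4.3.2 (bleeding times) also list it.

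**The concern.** ECG is the only safety measure with a summary specified in Section 6.4.3 that is not split by ethnic group, and the protocol gives no reason. The drug had not been given to Japanese subjects before, and ECG is one of the named means of assessing their safety. If the tables follow Section 6.4.3.4, a mean change in QTc or another ECG interval that is confined to one ethnic group, or larger in it, is averaged with the other group at the same dose. A reader of those tables could not tell whether the two groups behaved alike.

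**Working it through.** The protocol gives no figure for ECG precision or effect size, so there is none to reproduce. The precision figures in Section 6.5 concern AUC and Cmax and play no part here. The check compares the sections and then works out what pooling does to a mean.

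**Classification variables in Section 6.4.3**

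| Section | Data | Summarized by | Ethnic group? |
|---|---|---|---|
| 6.4.3.1 | Adverse events | SOC, preferred term, dose, ethnic group | Yes |
| 6.4.3.2 | Bleeding times | time after dose, dose, ethnic group | Yes |
| 6.4.3.3 | Laboratory, vital signs | dose, ethnic group, measurement time | Yes |
| 6.4.3.4 | ECG intervals | dose, visit, measurement time | No |
| 6.4.3.4 | QTc change | dose, assessment time | No |

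Visit cannot stand in for ethnic group. Under Section 3.4.2 both ethnic groups follow the same dose-by-visit schedule within a cohort, so each dose belongs to one visit and both groups fall in the same cell.

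**Cell sizes (Sections 3.4.2 and 6.5)**

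- Active, per dose: 8 Japanese + 8 Caucasian = 16. Each of the six doses is given in one cohort only.
- Placebo: 2 per cohort and ethnic group. Over two cohorts this is 2 × 2 = 4 per ethnic group, and 4 + 4 = 8 in all.

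**Effect of pooling**

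Let d_J and d_C be the mean shifts in Japanese and Caucasian active subjects at a dose.

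Pooled mean = (8 × d_J + 8 × d_C) / 16 = (d_J + d_C) / 2.

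If the shift occurs in Japanese subjects only (d_J = d, d_C = 0), the pooled mean is d/2. The shifts below are assumed for illustration and come from no document.

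| Assumed shift, Japanese only | Pooled mean shown |
|---|---|
| 5 ms | (8 × 5 + 8 × 0)/16 = 2.5 ms |
| 10 ms | (8 × 10 + 8 × 0)/16 = 5 ms |
| 20 ms | (8 × 20 + 8 × 0)/16 = 10 ms |

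The same halving applies to a shift in Caucasian subjects only, at every dose and for every interval.

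**Does another section restore the split?**

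- Section 6.2.4 defines change from baseline by dose level and does not mention ethnic group.
- Sections 4.4.10.5 to 4.4.10.9 cover recording, over-read and QT correction, not how the summaries are grouped.
- Section 3.1.7 has clinically significant ECG changes reviewed by dose group. Its explicit Japanese-Caucasian comparison covers laboratory measurements and adverse event rates.

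None of these adds ethnic group to the ECG tables.

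**The case against.** The strongest reply is that the matter belongs to the SAP. Section 4.4.10.1 leaves the types of serial-ECG comparison to it, Section 6.7 leaves data presentation to it, and Section 6.1 requires it to be final before unblinding. Section 6.4.3.4 does not forbid a further classification variable. This stands in part: the SAP could add ethnic group. But the protocol is not silent. It lists the variables for the ECG tables and omits the one it uses for the other safety summaries. Neither deferral calls that list provisional, so a SAP that follows it literally pools the groups.

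A reader might go further and infer that the ECG part of the primary objective goes unanswered, or that the trial yields no ECG result for Japanese subjects. The protocol does not support that:

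- The investigator reads every ECG as normal or abnormal, and abnormal tracings carry a comment on the CRF (Sections 4.4.10.1 and 4.4.10.5).
- Appendix B counts an abnormal electrocardiogram among the findings that can be an adverse event, and Section 6.4.3.1 summarizes adverse events by ethnic group.

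Nor would a heart-rate effect be hidden. Pulse is measured with the vital signs (Section 4.4.11), which Section 6.4.3.3 splits by ethnic group.

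A reader might also infer that a formal ethnic comparison of QTc was promised. Section 2.1 says assess for safety, and assess and compare only for pharmacokinetics and pharmacodynamics. Section 4.4.10.8 says QT analysis is descriptive and not a primary endpoint. The gap is therefore in descriptive tables, not a missing test.

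**Conclusion.** The point holds in a limited form. Section 6.4.3.4 states a rule that, taken literally, gives no ECG interval or QTc summary by ethnic group, in a study whose purpose is safety in Japanese subjects and whose primary objective names ECG. It is out of line with its three sibling sections. The defect is confined to these summaries; it is not an absence of all ECG safety information.

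Its size is a halving of any mean shift confined to one group. That follows from the planned equal numbers of 8 and 8. With unequal numbers, the factor is the affected group's share of the cell. The millisecond values are illustrations, and nothing in the protocol suggests that an ethnic difference in QTc is expected. The conclusion also assumes that the tables follow Section 6.4.3.4 as written; the SAP, which is not at hand, may already add the split. The change should be made, but no sample-size figure or planned test depends on it.

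**What to change.** In Section 6.4.3.4, have ECG intervals summarized *by dose, ethnic group, visit and measurement time*, and QTc change from baseline *by dose, ethnic group and assessment time*. This matches Section 6.4.3.3. The SAP should carry the same wording.

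The cost is two small text edits and one more classification variable in tables already planned. No new data, visits or subjects are needed. The only drawback is smaller cells: active cells fall from 16 to 8 per dose, the planned number in the other by-group safety tables, and placebo falls from 8 to 4 per ethnic group when pooled over cohorts. Sections 6.4.3.1 to 6.4.3.3 do not say how placebo is grouped, so they offer no model on that point; the grouping used for the ECG tables should be stated in the SAP.

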6.4.4 PK/PD relationships

The relationship between AZD6140, AR-C124910XX, total (AZD6140 + AR-C124910XX) concentrations and %PAI will be investigated using an E_{\max} model. Data from all doses within an ethnic group will be modeled simultaneously regardless of cohort. Observed and predicted %PAI versus exposure will also be presented graphically. The E_{\max} model is a non-linear model of the following form.

$$\% PAI = \frac{E_{\max} C^{\gamma}}{C^{\gamma} + EC_{50}^{\gamma}}$$

Models with sigmoidicity factor γ equal to 1 and where γ is estimated from the data will be explored. A model including a term for ethnicity will be used to explore the effect of ethnicity on model parameters.

6.5 Determination of sample size

Twenty Japanese subjects and 20 Caucasian subjects will be randomized into the trial. Ten subjects from each ethnic group will be assigned to each cohort. Eight subjects will be randomized to receive active AZD6140 (to achieve 6 evaluable) and 2 subjects will be randomized to receive placebo to AZD6140. The ratio of ethnic groups (Japanese/Caucasians) in terms of AUC and C_{\max} for the AZD6140 100 mg once daily doses can be estimated using a two-sided 90% confidence interval, assuming the following coefficients of variation (CV) (AUC: 21% C_{\max} : 20% [100 mg od based on trial 5130C5238]) with 6 subjects per ethnic group. Assuming these conditions hold, the log-scale precision for each of these intervals will be (0.2186 and 0.2092) and the 90% confidence interval around an observed ratio of 1 would be [AUC (0.80, 1.24) and C_{\max} (0.81, 1.23)].

6.6 Interim analyses

No interim analysis is planned.

6.7 Data Presentation

The details of data presentation will be provided in the SAP.

6.8 Data or safety monitoring committee (Not applicable for this protocol)

7. ETHICS

7.1 Ethics review

The final study protocol and the final version of the Written Informed Consent Form must be approved or given a favorable opinion in writing by the IEC or IRB as appropriate. The investigator must submit written approval to AstraZeneca before he or she can enroll any subject into the study.

The principal investigator is responsible for informing the IEC or IRB of any amendment to the protocol in accordance with local requirements. In addition, the IEC or IRB must approve all advertising used to recruit subjects for the study. The protocol must be reapproved by the IEC or IRB annually, as local regulations require.

Either the principal investigator(s) or AstraZeneca must submit progress reports to the IEC or IRB according to local regulations and guidelines. The principal investigator must also provide the IEC or IRB with any reports of serious adverse events from the study site.

Under no circumstances will the investigation be extended beyond the limitations defined in this protocol or any subsequent amendments.

The principal investigator is also responsible for providing the IRB with reports of any SAEs from any other study conducted with the investigational product. AstraZeneca will provide this information to the principal investigator(s).

7.2 Ethical conduct of the study

The study will be performed in accordance with the ethical principles that have their origin in the Declaration of Helsinki and are consistent with Good Clinical Practice, applicable regulatory requirements and the AstraZeneca policy on bioethics.

7.3 Subject information and consent

The principal investigator at each center will ensure that the subject is given full and adequate oral and written information about the nature, purpose, possible risk and benefit of the study. Subjects must also be notified that they are free to discontinue from the study at any time. The subject should be given the opportunity to ask questions and allowed time to consider the information provided.

The subject's signed and dated informed consent must be obtained before conducting any procedure specifically for the study.

The principal investigator must store the original, signed Written Informed Consent Form. A copy of the Written Informed Consent Form must be given to the subject. If modifications are made according to local requirements, the new version has to be approved by AstraZeneca.

7.4 Subject data protection

The Written Informed Consent Form will explain that study data will be stored in a computer database, maintaining confidentiality in accordance with national data legislation. All data computer processed by AstraZeneca will be identified by subject number/study code. The Written Informed Consent Form will also explain that for data verification purposes, authorized representatives of AstraZeneca, a regulatory authority, an IEC or IRB may require direct access to parts of the hospital or practice records relevant to the study, including subjects' medical history.

8.3 Procedures in case of overdose

There is limited previous human experience regarding the use of AZD6140. In case of overdose, monitoring of cardiac, hepatic and hematological effects is essential. Appropriate standard supportive therapy should be initiated. Since there is no specific antidote to this compound, subjects should be treated symptomatically. For further information see the Clinical Investigator's Brochure.

8.4 Procedures in case of pregnancy

Female subjects must be non-pregnant and of non-child bearing potential (surgically sterilized [eg. tubal ligation, hysterectomy, bilateral oophorectomy] or post menopausal for 12 months prior to screening).

Pregnancy itself is not regarded as an adverse event unless there is a suspicion that the investigational product under study may have interfered with the effectiveness of a contraceptive medication. However, the outcome of all pregnancies (spontaneous miscarriage, elective termination, normal birth or congenital abnormality) must be followed up and documented even if the subject is discontinued from the study.

All reports of congenital abnormalities/birth defects are SAEs. Spontaneous miscarriages should also be reported and handled as SAEs. Elective abortions without complications should not be handled as AEs. All outcomes of pregnancy must be reported to AstraZeneca on the pregnancy outcomes report form.

Appendix Date	

Appendix B
Additional Safety Information

DEFINITIONS OF ADVERSE EVENTS

Adverse event

An adverse event is the development of an undesirable medical condition or the deterioration of a pre-existing medical condition following or during exposure to a pharmaceutical product, whether or not considered causally related to the product. An undesirable medical condition can be symptoms (eg, nausea, chest pain), signs (eg, tachycardia, enlarged liver) or the abnormal results of an investigation (eg, laboratory findings, electrocardiogram). In clinical studies, an AE can include an undesirable medical condition occurring at any time, including run-in or washout periods, even if no study treatment has been administered.

Serious adverse event

A serious adverse event is an AE occurring during any study phase (eg, run-in, treatment, washout, follow-up), and at any dose of the investigational product, comparator or placebo, that fulfils one or more of the following criteria:

- results in death
- is immediately life-threatening
- requires in-subject hospitalization or prolongation of existing hospitalization
- results in persistent or significant disability or incapacity
- is a congenital abnormality or birth defect
- is an important medical event that may jeopardize the subject or may require medical intervention to prevent one of the outcomes listed above?

The causality of SAEs (eg, their relationship to study treatment) will be assessed by the investigator(s), who in completing the relevant case report form must answer “yes” or “no” to the question “Do you consider that there is a reasonable possibility that the event may have been caused by the drug?” Further guidance on the definition of a SAE and a guide to the interpretation of the causality question is provided in this Appendix to the Clinical Pharmacology Study Protocol.

Other significant adverse event (OAE)

OAEs will be identified by the Drug Safety Physician and if applicable also by the Clinical Study Team Physician during the evaluation of safety data for the Clinical Study Report. Significant adverse events of particular clinical importance, other than SAEs and those AEs leading to discontinuation of the subject from study treatment, will be classified as OAEs. Examples of these are marked hematological and other laboratory abnormalities, and certain events that lead to intervention (other than those already classified as serious), dose reduction or significant additional treatment. For each OAE, a narrative may be written and included in the Clinical Study Report.

Further guidance on the definition of a serious adverse event (SAE)

Life threatening

‘Life-threatening’ means that the subject was at immediate risk of death from the AE as it occurred or it is suspected that use or continued use of the product would result in the subject’s death. ‘Life-threatening’ does not mean that had an AE occurred in a more severe form it might have caused death (e.g. hepatitis that resolved without hepatic failure).

Hospitalization

Outpatient treatment in an emergency room is not in itself a serious AE, although the reasons for it may be (eg. bronchospasm, laryngeal edema). Hospital admissions and/or surgical operations planned before or during a study are not considered AEs if the illness or disease existed before the subject was enrolled in the study, provided that it did not deteriorate in an unexpected way during the study.

Important medical event or medical intervention

Medical and scientific judgment should be exercised in deciding whether a case is serious in situations where important medical events may not be immediately life threatening or result in death, hospitalization, disability or incapacity but may jeopardize the subject or may require medical intervention to prevent one or more outcomes listed in the definition of serious. These should usually be considered as serious.

Examples of such events are:

- Angioedema not severe enough to require intubation but requiring iv. hydrocortisone treatment
- Hepatotoxicity caused by paracetamol (acetaminophen) overdose requiring treatment with N-acetylcysteine
- Intensive treatment in an emergency room or at home for allergic bronchospasm
- Blood dyscrasias (eg, neutropenia or anemia requiring blood transfusion, etc.) or convulsions that do not result in hospitalization
- Development of drug dependency or drug abuse.

A guide to interpreting the causality question

The following factors should be considered when deciding if there is a “reasonable possibility” that an AE may have been caused by the drug.

- Time Course. Exposure to suspect drug. Has the subject actually received the suspect drug? Did the AE occur in a reasonable temporal relationship to the administration of the suspect drug?

- Consistency with known drug profile. Was the AE consistent with the previous knowledge of the suspect drug (pharmacology and toxicology) or drugs of the same pharmacological class? OR could the AE be anticipated from its pharmacological properties?
- Dechallenge experience. Did the AE resolve or improve on stopping or reducing the dose of the suspect drug?
- No alternative cause. The AE cannot be reasonably explained by another etiology such as the underlying disease, other drugs, other host or environmental factors.
- Rechallenge experience. Did the AE reoccur if the suspected drug was reintroduced after having been stopped? AstraZeneca would not normally recommend or support a rechallenge.
- Laboratory tests. A specific laboratory investigation (if performed) has confirmed the relationship?

A “reasonable possibility” could be considered to exist for an AE where one or more of these factors exist.

In contrast, there would not be a “reasonable possibility” of causality if none of the above criteria apply or where there is evidence of exposure and a reasonable time course but any dechallenge (if performed) is negative or ambiguous or there is another more likely cause of the AE.

In difficult cases, other factors could be considered such as:

- Is this a recognized feature of overdose of the drug?
- Is there a known mechanism?

Ambiguous cases should be considered as being a “reasonable possibility” of a causal relationship unless further evidence becomes available to refute this. Causal relationship in cases where the disease under study has deteriorated due to lack of effect should be classified as no reasonable possibility.

Clinical Pharmacology Study Protocol: Appendix C

Drug Substance	AZD6140
Study Code	D5130C05266
Edition No.	Final Version 1.0
